3.4.3 Prohibited concomitant medications

Prohibited concomitant medications	Corresponding protocol versions											
	V1.0	V1.1	V1.2 FRANCE	V1.2 GERMANY	V1.2 SWITZERLAND	V1.3 SWITZERLAND	V2.0	V3.0	V4.0	V4.2	V5.0 V5.1	
PPAR Gamma agonist, fibrates, ezetimibe, bile salts chelators, phytosterols, fish oils	X	X	X	X	X	X	X	X	X	X Specification of “PPAR Alpha agonists (fibrates)”	X Specification of “PPAR Alpha agonists (fibrates)”	X Specification of “PPAR Alpha agonists (fibrates)”
Glucagon like peptide-1 receptor agonists (liraglutide, exenatide),	X	X	X	X	X	X	X	X	X	X Adding “incl” before liraglutide, exenatide	X Adding “incl” before liraglutide, exenatide	X Adding “incl” before liraglutide, exenatide
Insulin							X	X	X	X	X	X
Vitamins E (alpha-tocopherol)	X Antioxidants such as vitamins E (alpha-tocopherol)	X Antioxidants such as vitamins E (alpha-tocopherol)	X Antioxidants such as vitamins E (alpha-tocopherol)	X Antioxidants such as vitamins E (alpha-tocopherol)	X Antioxidants such as vitamins E (alpha-tocopherol)	X Antioxidants such as vitamins E (alpha-tocopherol)	X Antioxidants such as vitamins E (alpha-tocopherol)	X Antioxidants such as vitamins E (alpha-tocopherol)	X Antioxidants such as vitamins E (alpha-tocopherol)	X	X	X
Anticoagulants (warfarin, dabigatran, rivaroxaban, apixaban)	X Anticoagulants without specification	X Anticoagulants without specification	X Anticoagulants without specification	X Anticoagulants without specification	X Anticoagulants without specification	X Anticoagulants without specification	X	X	X	X Adding “incl” before warfarin, dabigatran, rivaroxaban, apixaban	X Adding “incl” before warfarin, dabigatran, rivaroxaban, apixaban	X Adding “incl” before warfarin, dabigatran, rivaroxaban, apixaban
Steroids	X	X	X	X	X	X	X	X	X	X	X	X
Oral corticosteroids												X

### 3.4.4 Allowable medications for standard care or precautions

#### - **Obesity**

Stable weight since the liver biopsy was performed, defined by no more than a 5 % loss of initial body weight

#### - **Treatment used for the underlying medical condition**

Treatments are allowed within certain restrictions (described above and below) and provided they have been kept at **stable doses for at least 6 months before the pre-treatment biopsy.**

- *Type 2 diabetes*: Metformin is allowed as well as dipeptidyl peptidase-4 inhibitors and sodium-glucose transport protein 2 inhibitors: canagliflozin, dapagliflozin and empagliflozin. Glucagon like peptide-1 receptor agonists (liraglutide, exenatide) or glitazones are not allowed
- *Hyperlipidemia*: only statins at stable doses will be allowed
- *Antiplatelets agents*: The antiplatelets agents (aspirin, ticlopidine, clopidogrel, prasugrel, ticagrelor) are allowed
- *Herbal supplements and Others Supplementation*: Herbal preparations or vitamin supplements should not be taken as it is difficult to know exactly what they contain and could be liver toxic

#### - **Other Medications**

Medications other than the Investigational Medicinal Product (IMP) and those mentioned above must only be taken exceptionally and with the agreement of the investigator in order to avoid interference with study assessments. The need for other medication may lead to exclusion of the patient from the study.

If symptomatic medication is needed to treat adverse events related to IMP, the investigator will inform the sponsor about the concomitant medication given.

### 3.5 Changes in the conduct of the study

The last version of the protocol is version 5.1, dated March, 25th 2020. The original protocol was amended 7 times. The list of exhaustive changes is described in the summary of changes from each protocol amendment.

Additionally:

- It was initially planned to consider ‘at least 60’ sites, and finally 92 sites were involved in the study
- It was initially planned to consider ‘at least 300 patients screened’, and finally 868 patients were screened
- It was initially planned to randomise ‘225 patients’, and finally 247 were randomised in the study, mainly due to the multicentric nature of the study.
- As per initial sample size, it was estimated that 100 patients per group were needed to be screened to randomise 75 patients, meaning a screening failure rate of 25%. Based on collected data, the actual observed screening failure rate is of 72%.

The table below list the application date of each protocol version by country and site:

Country	Site	PI	V 1.0	V 1.1	V 1.2	V 1.3	V 2.0	V 3.0	V4.0	V4.2
			Version 28/AUG/2016	Version 19/AUG/2016	Version 10/FEB/2017 CH	Version 19/NOV/2017 CH	Version 10/MAR/2017	Version 02/AUG/2017	Version 02/NOV/2017	Version 12/DEC/2018
Australia	1201	[name]	NA	NA	NA	NA	NA	19/01/2018	11/04/2018	25/03/2019
Australia	1202	[name]	NA	NA	NA	NA	NA	22/12/2017	23/08/2018	29/04/2019
Australia	1203	[name]	NA	NA	NA	NA	NA	22/12/2017	12/06/2018	04/04/2019
Australia	1204	[name]	NA	NA	NA	NA	NA	22/12/2017	24/05/2018	25/03/2019
Australia	1205	[name]	NA	NA	NA	NA	NA	29/06/2018	22/08/2018	12/04/2019
Austria	1001	[name]	NA	28/02/2017	NA	NA	27/06/2017	10/11/2017	15/11/2018	11/01/2019
Austria	1002	[name]	NA	28/02/2017	NA	NA	27/06/2017	15/11/2017	15/11/2018	11/01/2019
Belgium	1	[name]	NA	23/01/2017	NA	NA	15/05/2017	16/10/2017	23/05/2018	11/01/2019
Belgium	2	[name]	NA	23/01/2017	NA	NA	15/05/2017	16/10/2017	23/05/2018	11/01/2019
Belgium	3	[name]	NA	23/01/2017	NA	NA	15/05/2017	16/10/2017	23/05/2018	11/01/2019
Belgium	4	[name]	NA	NA	NA	NA	NA	09/02/2018	19/06/2018	11/01/2019
Belgium	5	[name]	NA	NA	NA	NA	NA	09/02/2018	23/05/2018	11/01/2019
Canada	1301	[name]	NA	NA	NA	NA	NA	15/12/2017	30/07/2018	27/02/2019
Canada	1302	[name]	NA	NA	NA	NA	31/07/2017	12/10/2017	18/04/2018	16/01/2019
Canada	1303	[name]	NA	NA	NA	NA	16/08/2017	04/10/2017	11/07/2018	12/02/2019
Canada	1304	[name]	NA	NA	NA	NA	11/10/2017	31/10/2017	09/07/2018	05/03/2019
Canada	1305	[name]	NA	NA	NA	NA	16/06/2017	13/10/2017	31/05/2018	26/02/2019

## 4 Statistical methods

### 4.1 General statistical considerations

#### 4.1.1 *Software used*

All statistical analyses will be performed with the SAS® software version 9.4 or higher.

#### 4.1.2 *Statistical deliverables*

Statistical results will be delivered in several batches:

- the first batch will contain the Head Line Results (HLR)
- the other batches being all other results described in this Statistical Analysis Plan (SAP).

The contents of the HLR and other results are defined in Appendix 2 - Contents of statistical deliverables.

#### 4.1.3 *Statistical quality control*

##### Derived datasets

For most important derived datasets an independent double programming will be performed (Quality Control (QC) type 3): for a given derived dataset, 2 programmers independently write a program to produce the dataset; then the 2 datasets obtained by the 2 programmers are compared using the SAS® COMPARE procedure; content as well as structure of the 2 datasets should be 100% similar. For other datasets a simple control will be performed. Appropriate documentation of QC will be developed.

The following deliverables will be provided at time of final analysis:

- Specifications for derived datasets
- Analysis datasets in SAS format
- SAS programs generating the derived datasets

##### Tables Listing Figures (TFLs)

All SAS programs and TFLs will be programmed and quality controlled by the study SAS programmer (self-inspection of the programs/logs and results).

Additionally a QC will be performed by the study biostatistician:

- Simple programming for all HLR tables (QC type 2): study biostatistician will use some SAS® procedures which allow verifying the statistical results obtained
- Review of the program and the associated statistical output(s) for non HLR TFLs (QC type 1): check of the mean, the standard deviation, the minimum, the maximum for quantitative variables, the frequencies and the percentages for the qualitative variables and the size of the populations

Appropriate documentation of QC will be developed.

The following deliverables will be provided at time of final analysis:

- Two separate documents compiling all TLFs: one for Appendix 14 and another one for Appendix 16.2
- SAS programs generating the outputs: TFLs

The detailed strategy put in place for HLRs QC (from derived datasets to TFLs) is provided in “

See appended document: INVENTIVA\_NATIVE\_SAP\_Mock\_Up\_TFLs

Appendix 3 – Strategy for analysis QC” of this document.

#### *4.1.4 Descriptive statistics*

Continuous variables will be described using: number of non-missing observations (N), number of missing observations (Nmiss), arithmetic mean (Mean), standard deviation (SD), minimum (MIN), quartile 1 (Q1), median (Median), quartile 3 (Q3) and maximum (MAX).

MIN, Q1, Median, Q3 and MAX will be given at the data number of decimal points but limited to 2 decimals. Mean and SD will be given at 1 additional decimal point but limited to 3 decimals.

The 95% two-sided confidence interval (CI) will be calculated when appropriate using the standard method (Standard normal distribution).

Categorical variables will be presented using N, Nmiss and percentages (%). Missing data will not be included in the denominator for the calculation of percentages.

Proportions will be displayed with one decimal.

The 95% two-sided CIs will be calculated when appropriate using the exact (Clopper-Pearson) method.

All descriptive statistics will be done by treatment group (Placebo, lanifibranor 800 mg/day and 1200 mg/day) and overall (for baseline characteristics only).

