#### - Descriptive analysis

Fasting glucose and HbA1c assessed at Screening, Baseline, Week 4, Week 14, Week 24 and Week 28, as well as insulin, C-peptid, fructosamide and HOMA index assessed at Week 0 and Week 24, will be described over time using descriptive statistics by treatment group and diabetic status, in terms of:

- Raw values
- Absolute change from baseline

The 95% CI of the mean will also be provided.

- Status over time (Normal-Normal, Normal-Abnormal, Abnormal-Normal, Abnormal-Abnormal)

The 2 timepoints prior to first intake will have to be analysed: screening and baseline.

One graph will also be provided describing the raw values (with 95% CI) by treatment group over time (including screening values)

The HOMA index will also be described qualitatively over time using descriptive statistics by treatment group and diabetic status (HOMA < 3, ≥ 3).

- Absolute changes in HbA1c value will be described qualitatively over time using descriptive statistics by treatment group and diabetic status:
  - o Decrease of HbA1c (Decrease of 1%, No change (Change within ]-1% ; 1%[]), Increase ≥ 1%).
  - o Decrease of HbA1c (Decrease ≥ 0.5%, No change (Change within ]-0.5% ; 0.5%[]), Increase ≥ 0.5%)
- Evaluation of treatment effect (each dose versus placebo)

For fasting glucose, HbA1c, insulin and HOMA index, in order to evaluate each treatment dose versus placebo at week 24, a MMRM will be performed as detailed in section 4.1.5.

In order to take into account multiplicity of tests, the ascending Hochberg procedure will be applied (see section 4.1.5 for details).

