**Sensitivity analysis**

None

**Analysis by subgroups** (descriptive analysis only)

- By diabetic status (Yes, No) for fasting glucose, insulin, C-peptid, HOMA index, fructosamide and HbA1c
- By HbA1c at baseline ( $\leq 6.5\%$ ,  $>6.5\%$ ) for HbA1c

*5.2.3.9 Liver enzymes*

The following table describes for each parameter the collection time and the type of analyses to be done.

Parameter	Collection time	Main analyses (see section 5.2.3.8 describing the methodology)	Sensitivity analyses	Subgroup analyses
ALT	Screening, Baseline, weeks 4, 14, 24 and 28	Descriptive analysis Treatment effect ( each dose versus placebo ) Time course of the response of each treatment group	None	By diabetic status (Yes, No)
AST	Screening, Baseline, weeks 4, 14, 24 and 28	Descriptive analysis Treatment effect ( each dose versus placebo ) Time course of the response of each treatment group	None	By diabetic status (Yes, No)
GGT	Screening, Baseline, weeks 4, 14, 24 and 28	Descriptive analysis Treatment effect ( each dose versus placebo ) Time course of the response of each treatment group	None	By diabetic status (Yes, No)
Alkaline Phosphatase	Screening, Baseline, weeks 4, 14, 24 and 28	Descriptive analysis	None	By diabetic status (Yes, No)
Total Bilirubin	Screening, Baseline, weeks 4, 14, 24 and 28	Descriptive analysis	None	By diabetic status (Yes, No)

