## 5.2.3.10 Plasma lipids levels

The following table describes for each parameter the collection time and the type of analyses to be done.

Parameter	Collection time	Main analyses (see section 5.2.3.8 describing the methodology)	Sensitivity analyses	Subgroup analyses
Total Cholesterol	Screening, Baseline, weeks 4, 14, 24 and 28	Descriptive analysis Treatment effect ( each dose versus placebo ) Time course of the response of each treatment group	None	By diabetic status (Yes, No) By Statins at baseline (Yes, No)
HDL-C	Screening, Baseline, weeks 4, 14, 24 and 28	Descriptive analysis Treatment effect ( each dose versus placebo ) Time course of the response of each treatment group	None	By diabetic status (Yes, No) By Statins at baseline (Yes, No)
LDL-C	Screening, Baseline, weeks 4, 14, 24 and 28	Descriptive analysis Treatment effect ( each dose versus placebo ) Time course of the response of each treatment group	None	By diabetic status (Yes, No) By Statins at baseline (Yes, No)
Triglycerides	Screening, Baseline, weeks 4, 14, 24 and 28	Descriptive analysis Treatment effect ( each dose versus placebo ) Time course of the response of each treatment group	None	By diabetic status (Yes, No) By Statins at baseline (Yes, No)
Apo A1	Baseline, week 24	Descriptive analysis Treatment effect ( each dose versus placebo )	None	By diabetic status (Yes, No) By Statins at baseline (Yes, No)
FFA	Baseline, week 24	Descriptive analysis	None	By diabetic status (Yes, No) By Statins at baseline (Yes, No)
Adiponectin	Baseline, week 24	Descriptive analysis Treatment effect ( each dose versus placebo )	None	By diabetic status (Yes, No) By Statins at baseline (Yes, No)
Leptin	Baseline, week 24	Descriptive analysis	None	By diabetic status (Yes, No) By Statins at baseline (Yes, No)
APO B	Baseline, week 24	Descriptive analysis	None	By diabetic status (Yes, No) By Statins at baseline (Yes, No)

Parameter	Collection time	Main analyses (see section 5.2.3.8 describing the methodology)	Sensitivity analyses	Subgroup analyses
APO C3	Baseline, week 24	Descriptive analysis	None	By diabetic status (Yes, No) By Statins at baseline (Yes, No)
FGF21	Baseline, week 24	Descriptive analysis	None	By diabetic status (Yes, No) By Statins at baseline (Yes, No)

Only fasting results will be considered for analyses.

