### **Main analysis**

The population of analysis will be the Safety Set as described in section 4.3.4. Only the observed cases under treatment will be analysed (see section 4.1.6.3).

- Descriptive analysis

Each parameter will be described at each study visit using descriptive statistics by treatment group in the safety set of patients, in terms of:

- Raw values
- Absolute change from Baseline
- Status over time (Normal-Normal, Normal-Abnormal, Abnormal-Normal, Abnormal-Abnormal)

Then, for each parameter, will be provided a graph reporting the mean (95% CI) of the parameter by visit and treatment group.

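### SAP 4.1.4 specifies the normal distribution for 95% confidence intervals of means although the SD is estimated, so these descriptive intervals are slightly too narrow

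*SAP*

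**What the plan says.** SAP section 4.1.4 sets the rule for all descriptive statistics. Continuous variables are summarised with, among others, the "arithmetic mean (Mean), standard deviation (SD"), and the interval rule reads: "The 95% two-sided confidence interval (CI) will be calculated when appropriate using the standard method (Standard normal distribution"). No known or external SD appears anywhere in the SAP, and the section does not mention a t quantile. Proportions are given Clopper-Pearson intervals in the same section.

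The rule is then used in several places:

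- Section 5.2.3.8 (glucose metabolism) says that the markers "will be described over time using descriptive statistics by treatment group and diabetic status, in terms of" raw values and change from baseline, and adds: "The 95% CI of the mean will also be provided". A graph of raw values with 95% intervals by treatment group is also planned.
- The tables for liver enzymes, lipids, inflammatory, fibrosis and chemistry markers (5.2.3.9 to 5.2.3.13) and for bone markers (5.3.3.2) refer to 5.2.3.8 for the method of their main analyses.
- Section 5.3.3.3 (safety laboratory tests) plans "a graph reporting the mean (95% CI) of the parameter by visit and treatment group". Similar plots are planned for weight (5.3.3.4), QTcF and heart rate (5.3.3.5) and quality-of-life scores (5.4).

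**The concern.** When the SD is estimated from the same n observations as the mean, the standardised mean of normal data follows a t distribution on n−1 degrees of freedom. Using 1.960 in place of the t quantile ignores the uncertainty in the SD, so an interval labelled 95% has lower coverage, and the shortfall grows as n falls.

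What is at stake is accurate labelling of error bars and tabulated intervals, not a test result. It has some weight because several markers are only described, even at full-arm level: free fatty acids, leptin, the interleukins and the TIMPs, for example. For these, the descriptive interval is the only confidence interval planned. In addition, the checks that SAP 4.1.3 lists for tables outside the headline results cover means, SDs, ranges, frequencies, percentages and population sizes. Interval limits are not named, so that check would not necessarily catch a wrong quantile.

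**Working it through.** The SAP gives no numerical figure for these intervals, so there is none of its own to reproduce. The check is on what the stated rule delivers.

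**Inputs**

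- Normal quantile for a two-sided 95% interval: 1.960 (SAP 4.1.4 names the distribution; the number follows from it).
- Patients randomised: 247 (SAP 3.5), allocated 1:1:1 (SAP 3.2). 247 / 3 = 82.3, so about 82 per arm.
- Largest possible size of the smaller part when an arm of 82 is split in two by diabetic status: 82 / 2 = 41.
- Subgroup rule in SAP 4.7: no subgroup analysis if a category holds less than 15% of patients. 0.15 × 247 = 37.05 patients in total; 37.05 / 3 = 12.35, so about 12 per arm if spread evenly.
- Actual subgroup sizes: not in the documents. The values below 41 are therefore assumptions, shown as a range.

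**Formulas, for normal data**

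- Interval as written: mean ± 1.960 × s / √n.
- True coverage = 2 × F(1.960; n−1) − 1, where F is the t distribution function on n−1 degrees of freedom.
- Width of the t interval relative to the planned one = t(0.975; n−1) / 1.960.

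**Results**

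| n per cell | What it represents | t(0.975; n−1) | Coverage of planned interval | t interval wider by |
|---|---|---|---|---|
| 82 | full arm | 1.990 | 94.7% | 1.5% |
| 41 | largest possible smaller part of a split arm | about 2.02 | about 94.3% | about 3.1% |
| 20 | assumed | 2.093 | 93.5% | 6.8% |
| 12 | assumed; approximate 15% floor, if that rule applies | 2.201 | 92.4% | 12.3% |

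As an example of the last column, 2.201 / 1.960 = 1.123.

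The numbers actually analysed can be lower than these. Section 5.2.3.8 uses only observed cases under treatment and, for some markers, only fasting values.

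**The case against.** **The wording may be loose.** The phrase can be read as ordinary normal-theory intervals, in contrast to the exact method for proportions. The SAP never writes 1.96 or a formula, and the appended table shells are not available to settle it. This reading is possible, but nothing in the documents states it. A programmer who follows the text literally would use the normal quantile. If t was meant, the words still need changing.

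**The plots are by full arm.** This stands. The graphs in 5.2.3.8 and 5.3.3.3 are by treatment group and visit, where the difference is 1.5% of width, and 5.3.3.3 plans no subgroup analysis at all.

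**The reach into small subgroups is limited.** This also stands. A reader might infer that the SAP plans badly undersized intervals in statin and HbA1c subgroups, since it lists "By HbA1c at baseline" for HbA1c and "By Statins at baseline (Yes, No") for lipids. The text does not go that far. The instruction to give an interval of the mean sits in the main analysis, by treatment group and diabetic status. The subgroup part of 5.2.3.8 says only "descriptive analysis only", and in the lipid table the cross-reference for method heads the main-analyses column. Where the SAP wants subgroup intervals it says so, as for the primary endpoint in 5.2.2.3. Nor do the documents show that any of these subgroups is small.

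**Readers can recompute.** N and SD are tabulated with each mean, so the planned interval is not the only information on precision.

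**No inference depends on these intervals.** This is correct. The primary analysis is a CMH test, the mixed models for repeated measures use Kenward-Roger degrees of freedom (SAP 4.1.5), and the descriptive subgroups carry no test or decision rule.

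**Conclusion.** The point holds, and it is minor. As written, SAP 4.1.4 yields 95% intervals for means that are narrower than the t interval at every n. The shortfall is 0.3 percentage points of coverage at full-arm size. In the smaller part of an arm split by diabetic status, it is about 0.7 points or more. It reaches 2.6 points only if a cell is as small as about 12. That size is an assumption: it depends on the 15% rule in SAP 4.7 applying, which is unclear because the diabetic-status tables belong to the main descriptive analysis and neither statin use nor baseline HbA1c is in that section's list.

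The coverage figures assume normal data. It would be wrong to infer that the trial's efficacy conclusions are affected: the CMH tests, the Clopper-Pearson intervals and the repeated-measures comparisons do not use this rule.

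**What to change.** In SAP 4.1.4, replace the standard normal distribution with Student's t distribution on n−1 degrees of freedom for confidence intervals of means, and state that this applies to tables and graphs alike.

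The cost is a few words in the SAP and slightly wider intervals. No hypothesis test, sample size or data collection changes. For markedly skewed markers the t interval does not by itself guarantee 95% coverage, so the change should not be presented as doing so.

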#### *4.1.5 Treatment groups comparison*

For statistical tests, the type I error risk of these will be set at 5% (2-sided) without adjustments for multiplicity testing, unless specified otherwise.

P-values will be presented with 3 decimals. Any p-value less than 0.001 will be presented as <0.001, even if it would normally round up to 0.001.

#### **Hochberg procedure for multiplicity testing**

When specified, the ascending Hochberg procedure will be used to adjust for multiplicity testing. This procedure is a powerful tool that decreases the false discovery rate: this is the expected proportion of "discoveries" (significant results) that are actually false positives. Adjusting the rate helps to control for the fact that sometimes small p-values (less than 5%) happen by chance, which could lead to incorrectly reject the true null hypotheses. In other

words, the procedure helps to avoid type I errors (false positives). To run the procedure, the following steps will be followed:

1. Put the individual p-values (without multiplicity adjustment) in ascending order, from smallest to largest.
2. Assign ranks to the p-values. For example, the smallest has a rank of 1, the second smallest has a rank of 2.
3. Calculate each individual p-value's critical value, using the formula  $(i/m)Q$ , where:
  - $i$  = the individual p-value's rank,
  - $m$  = total number of tests,
  - $Q$  = the false discovery rate (type I error)
4. Compare original p-values to the critical ones from Step 3; find the largest p value that is smaller than the critical value.

As an example, the following table shows the result of 2 tests (*lanifibranor 800 mg vs. placebo* and *lanifibranor 1200 mg vs. placebo*) with their p-values. The list of p-values are ordered (Step 1) and then ranked (Step 2) in the 3rd column. The last column shows the calculation of the critical value with a false discovery rate of 5% (Step 3). For instance, last column for test 2 (*lanifibranor 800 mg vs. placebo*) is calculated as  $(2/2) * 0.05 = 0.050$ :

Test	p-value observed	Rank (i)	$(i/m)Q=(i/2)x0.05$
Lanifibranor 1200 mg vs. placebo	0.020	1	0.025
Lanifibranor 800 mg vs. placebo	0.028	2	0.050

As the p-value associated to the test "*lanifibranor 1200 mg vs. placebo*" (p-value = 0.020) is smaller than its associated critical value (critical-value = 0.025), the test is considered as statistically significant after multiplicity adjustment according to the ascending Hochberg procedure. Similarly, the test "*lanifibranor 800 mg vs. placebo*" is considered as statistically significant after multiplicity adjustment according to the ascending Hochberg procedure: p-value = 0.028 < critical-value = 0.050.

Comparison of treatment groups for **quantitative variables** will be performed using:

- an Analysis of Covariance (**ANCOVA**) using the SAS MIXED procedure with the treatment and the diabetic status as covariates when specified

Or

- a Mixed Model for Repeated Measures (**MMRM**) when specified using the SAS MIXED procedure with:
  - a. The absolute change from baseline of the analysis variable as endpoint (MODEL statement of the MIXED procedure)
  - b. The time, treatment, the diabetic status, the interaction (treatment \* time) and the baseline value as fixed effects (MODEL statement of the MIXED procedure). Time, treatment and diabetic status being considered as categorical variables
  - c. A time repeated measure (REPEATED statement of the MIXED procedure) within each subject (SUBJECT = subject as option of the REPEATED

statement). An unstructured (type=UN) variance covariance matrix being used as option of the REPEATED statement

- d. The Kenward-Roger approximation to estimate denominator degrees of freedom and adjust standard errors (ddfm=kr option in MODEL statement)

In order to explore the validity of the model (and more accurately the assumption regarding independence, normality and constant variance of residuals), the following graphs will be provided: Q-Q plot of the residuals, distribution of residuals with its corresponding normal density estimate and scatterplot of residuals vs. predicted values.

With such models (ANCOVA, MMRM) different treatment effects will be evaluated:

- **Evaluation of treatment effect (Each dose vs. placebo) at week 24:** In order to evaluate each treatment dose versus placebo at week 24 the following contrasts of interest will be used:
  - o 800 mg/day vs. placebo: -1 for Placebo, 1 for 800 mg/day and 0 for 1200 mg/day
  - o 1200 mg/day vs. placebo: -1 for Placebo, 0 for 800 mg/day and 1 for 1200 mg/day.

In order to take into account multiplicity of tests, the ascending Hochberg procedure will be applied (see section 4.1.5).

- **Evaluation of dose effect (800 mg vs. 1200 mg) at week 24:** In order to evaluate the dose of 800 mg/day versus the dose of 1200 mg/day at week 24 the following contrast of interest will be used:
  - o 800 mg/day vs. 1200 mg/day: 0 for Placebo, -1 for 800 mg/day and 1 for 1200 mg/day
- **Time course of the response of each treatment group:** In order to evaluate the time course of the response of each dose (separately) at each time-point the following contrasts of interest will be used for each dose:
  - o week 4 vs. week 14: -1 for week 4, 1 for week 14, 0 for week 24 and 0 for week 28
  - o week 4 vs. week 24: -1 for week 4, 0 for week 14, 1 for week 24 and 0 for week 28
  - o week 4 vs. week 28: -1 for week 4, 0 for week 14, 0 for week 24 and 1 for week 28
  - o week 14 vs. week 24: 0 for week 4, -1 for week 14, 1 for week 24 and 0 for week 28
  - o week 14 vs. week 28: 0 for week 4, -1 for week 14, 0 for week 24 and 1 for week 28
  - o week 24 vs. week 28: 0 for week 4, 0 for week 14, -1 for week 24 and 1 for week 28

In order to take into account multiplicity of tests, the ascending Hochberg procedure will be applied (see section 4.1.5).

Lowest dose will always be considered as reference for treatment effect calculation. As well as earliest visit will always be considered as reference for time course evaluation.

Comparisons of treatment groups for **qualitative variables** will be done using the FREQ procedure with Cochran–Mantel–Haenszel (CMH) test option, stratified on the diabetic status at Baseline (yes/no). The primary measure of the effect size will be the CMH odds ratio with an adjustment for diabetic status. Because the odds ratio is not easy to interpret when the rate of responders in the placebo group is not very small the odds ratio (OR) will be converted in

Risk Ratio (RR) using the following formula  $RR = (P1/P0) = OR/[(1-P0) + (P0 \times OR)]$ . The same formula will be applied to OR 95% CI lower and upper bounds to obtain RR 95% CI. The log-binomial model will preferentially be used in the absence of convergence or estimability issue for estimating the effect size with RR. The primary handling of heterogeneity of result across strata will be performed through the Breslow-Day test. If the homogeneity hypothesis is rejected, then the estimate of the difference in percentage points between each dose and placebo along with the 95% C.I. will be provided within each stratum, as well as the p-value of the association test between treatment and qualitative variable (Chi-2 test or Fisher's exact test). If the interaction between stratum and treatment (Breslow Day test) is significant it means that the treatment effect has not the same magnitude in diabetic and non-diabetic patients. In the absence of qualitative interaction there will be no further adjustment of the type one error for multiplicity of testing. Smallest dose will always be considered as reference for OR/RR calculation.

Dose-response relationship for **qualitative variables** will be estimated using the Cochran-Armitage trend test via the LOGISTIC procedure (See Reference 5). Within this model, dose will be considered as a quantitative covariate (0 mg, 800 mg and 1200mg) and diabetic status as a qualitative covariate (Presence, Absence). The p-value assessing the significant dose-response relationship at week 24 will be provided based on this model (Score test).

